### 5.2 EXCLUSION CRITERIA

A patient will be excluded from the study if:

1. They are unable to answer the 3 study competency questions that indicate capability of providing consent.

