## 4 STUDY DESIGN

### 4.1 OVERALL DESIGN

The primary objective of this pragmatic clinical trial is to replicate POINT at two new hospitals and establish POINT's effectiveness compared to standard care. In doing so, we aim to understand POINT's effect on the recovery process, including treatment and recovery outcomes and overdose. We hypothesize that POINT patients will engage in MOUD at higher rates, remain in treatment longer, and have significantly improved outcomes in comparison to the standard care group.

Hospital patients meeting the eligibility criteria at one of the two participating EDs are approached by a recovery coach or research assistant and invited to enroll in the study. Participants of the study are randomly enrolled into one of two study arms: (1) the POINT intervention arm, in which they receive ongoing recovery support services from a recovery coach or (2) the control arm, in which they receive a list of available local resources for substance use disorder from the research assistant. The study utilizes shift-level randomization, and each day of enrollment is separated into three enrollment shifts which are randomly assigned to one of the two study arms. Thus, participants' arm assignment is pre-determined by the shift in which they are discharged from the ED and enrolled into the study.

Participants are asked to complete a single structured interview at the time of their enrollment and are followed longitudinally only through administrative data, which is collected for participants from three years prior to their enrollment through two years following their enrollment.

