## 5 STUDY POPULATION

### 5.1 INCLUSION CRITERIA

To be eligible for the study, a patient must:

1. Be revived from a drug overdose or admitted to the ED for an opioid-related health issue, including opioid withdrawal, abscess (from IV opioid use), endocarditis (from IV opioid use), or active opioid intoxication.
2. Score at least “1” on the opioid use disorder screening tool.
3. Be eligible for discharge from one of the two participating EDs and deemed able to speak to research staff by ED staff.
4. Be age 18 or older.
5. Be medically stable (i.e., cleared to leave the ED by a physician) and capable of providing consent.

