## 6.3 MEASURES TO MINIMIZE BIAS: RANDOMIZATION AND BLINDING

The study is randomized at the enrollment shift level. Each day of study enrollment is broken into three shifts (8am-3:59pm, 4pm-11:59pm, 12am-7:59am). In advance, each shift is randomly assigned to one of the two enrollment arms (i.e., POINT or control) to determine whether patients discharged during these times will enroll into the POINT arm or the standard care arm. Any individual who is cleared for discharge from the ED for an overdose or for an opioid-related health issue, including opioid withdrawal, abscess (from IV drug use) or active opioid intoxication will be eligible for the study. As determined by the preset randomization, recovery coaches (RC) will engage with patients cleared for discharged from the ED during the POINT shifts and research assistants (RA) will engage with patients cleared for discharged from the ED during control shifts.

Additional note: The study sites plan to implement Project POINT regardless of the research study. We are not modifying any aspect of POINT for the study purposes. Therefore, all recovery coach duties

(baseline administrative data collection, provision of naloxone, patient follow-up) are part of POINT prescribed services that would be carried out regardless of the research. We are randomizing the shift POINT is delivered on to take advantage of the fact that they are not able to fully staff all hospital shifts with a recovery coach--thus allowing us to test the intervention's effectiveness. Only those patients in the standard care arm will be asked to complete data collection activities that would not be completed outside of the research study.

Sample randomization for week of services								
Week	Shift	Day						
		Mon	Tue	Wed	Thu	Fri	Sat	Sun
1	8am-3:59pm	RC	RA	RA	RC	RC	RC	RA
	4pm-11:59am	RA	RC	RC	RA	RA	RA	RC
	12am-7:59am	RC	RA	RA	RC	RA	RA	RC

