## 9 STATISTICAL CONSIDERATIONS

## 9.1 STATISTICAL HYPOTHESES

Primary Endpoint:

- Overdose Admissions
  - [Measured: 1 year pre-enrollment through 1 year post-enrollment]

We hypothesize that, compared to patients in the control condition, patients receiving the POINT intervention will experience fewer subsequent admissions to the ED for overdose.

Secondary Endpoints:

- MOUD Engagement
  - [Measured: 1 year pre-enrollment through 1 year post-enrollment]
- Duration of MOUD Engagement
  - [Measured: 1 year pre-enrollment through 1 year post-enrollment]
- ED Admissions
  - [Measured: 1 year pre-enrollment through 1 year post-enrollment]
- Inpatient Hospital Admissions
  - [Measured: 1 year pre-enrollment through 1 year post-enrollment]
- Time to Relapse
  - [Measured: Enrollment through 1 year post-enrollment]
- Medicaid Enrollment for Participants Without Insurance
  - [Measured: Enrollment through 1 year post-enrollment]
- Child Welfare Involvement
  - [Measured: 3 years pre-enrollment through 1 year post-enrollment]
- Incarceration
  - [Measured: 3 years pre-enrollment through 1 year post-enrollment]

We hypothesize that, compared to patients in the control condition, patients receiving the POINT intervention will experience better recovery outcomes (i.e., higher MOUD engagement and longer duration of engagement, lower ED and inpatient admissions, longer times between relapse, higher Medicaid enrollment for those without insurance, lower child welfare involvement, and lower incarceration).

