### 9.3 POPULATIONS FOR ANALYSES

All participants consented to the trial will be included in the analyses.

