#### 9.4.2 ANALYSIS OF THE PRIMARY ENDPOINT(S)

Questions	Defined/explained
Primary endpoint	
Describe how the primary endpoint is calculated, if not readily apparent	Change in Overdose Admissions: Using electronic health records, it is calculated as the total combined number of overdoses resulting in an emergency department presentation within the specified time period.
Describe the scale (nominal/binary/categorical, ordinal, interval); state if it is measured as a single endpoint/summary measure or repeated measure	binary
Describe the statistical procedure(s) that will be used to analyze the primary endpoint (e.g., multiple regression, repeated measures mixed models, logistic regression, Analysis of Covariance (ANCOVA)). Describe the covariates and factors in the model. Provide a rationale for covariates and how they will be selected to achieve a parsimonious model. If the decision to specify covariates is deferred for the SAP, indicate here.	Summarized using frequencies and percentages and then compare arms using the Fisher's exact test.
Describe how results of statistical procedure(s) will be presented (e.g., adjusted means (Least-squares means (LSMEANS)) with standard errors, odds ratios with 95% confidence intervals, prevalence rates, number-needed-to-treat)	Presented using frequencies and percentages
Describe details to check assumptions required for certain types of analyses (e.g., proportional hazards, transformations or, when appropriate, nonparametric tests)	The nonparametric Fisher's exact test is used to compare the primary endpoint.
Describe the Populations for which the analysis will be conducted, as discussed in Section 9.3, Populations for Analyses	All study participants
Describe how missing data will be handled (e.g., type of imputation technique, if any, and provide justification), and approach to handling outliers, non-adherence and lost to follow-up	We do not expect there to be a large amount of missing data due to the use of administrative datasets. However, missing values may occur when subjects die during the specified time period. Sensitivity analysis is performed by excluding subjects who die during the specified time period.

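### No rule bars people already enrolled: a returning participant can be enrolled again, possibly in the other arm, and returning controls may be offered POINT during follow-up

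*Combined protocol and SAP*

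**What the plan says.** Section 5.2 has one exclusion criterion: "They are unable to answer the 3 study competency questions that indicate capability of providing consent". Section 5.1 opens entry to patients who must "Be revived from a drug overdose or admitted to the ED for an opioid-related health issue", and section 6.3 extends eligibility to anyone cleared for discharge after such a visit. Sections 5.1, 5.4, 5.5 and 8.1 do not ask whether the patient is already a participant.

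Assignment is by shift. Section 4.1 says that a participant's "arm assignment is pre-determined by the shift in which they are discharged from the ED and enrolled into the study". Under section 6.3, "recovery coaches (RC) will engage with patients cleared for discharged from the ED during the POINT shifts", and research assistants do the same on control shifts. The same section says that the sites would run POINT whether or not the study took place.

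The primary endpoint is described in section 9.4.2 as the "total combined number of overdoses resulting in an emergency department presentation within the specified time period", but its scale is given there as binary. The analysis is "Summarized using frequencies and percentages and then compare arms using the Fisher's exact test". Section 9.1 gives the window as "Measured: 1 year pre-enrollment through 1 year post-enrollment". On the analysis population, section 9.3 says only: "All participants consented to the trial will be included in the analyses".

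**The concern.** An overdose seen in a participating ED is both a way into the trial and the primary outcome event. Because the arm belongs to the shift and not to the person, each return visit draws a new arm. Two problems follow.

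The first is repeat enrollment. A person enrolled twice within a year contributes two records with overlapping windows. One overdose can be an outcome for the first record and the index event for the second, and the second record's pre-enrollment year can cover the first record's follow-up. Fisher's exact, Wilcoxon and log-rank tests all assume independent subjects. If the first enrollment was in POINT and the second falls on a control shift, the new control record is already exposed on day 0, since sections 6.1.1 and 6.1.2 let POINT patients re-engage at any time.

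The second is crossover without re-enrollment. A control who returns on a POINT shift may be offered coaching within the follow-up year. No section says how such contact is recorded or reported.

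**Working it through.** **1. The plan's sample size.** Inputs from section 9.2: 12% control rate, 6-point reduction (so 6% in POINT), 80% power, 5% significance (taken as two-sided). With pooled variance and no continuity correction:

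n = [1.960 × √(2 × 0.09 × 0.91) + 0.842 × √(0.12 × 0.88 + 0.06 × 0.94)]² / 0.06² = (0.793 + 0.339)² / 0.0036 ≈ 356 per arm.

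This matches the stated 356. The calculation has no allowance for crossover or repeat records.

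**2. Does a returning participant qualify again?** Take a control enrolled in month 0 who overdoses in month 3. The entry event in 5.1 is met. The screening score, age, stability and consent conditions can all be met again. The exclusion in 5.2 does not apply. Under 4.1 and 6.3 the arm is that of the new discharge shift. Nothing in the stated rules stops a second enrollment.

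**3. Controls who could meet a coach through an overdose return.**
- Controls with a follow-up overdose: 356 × 0.12 = 42.7.
- Cleared on a POINT shift, assuming one half: 42.7 × 0.5 = 21.4, or 6.0% of 356. The sample week in 6.3 has 10 coach shifts out of 21, close to one half.
- If half present at other hospitals (assumption): 10.7, or 3.0%.
- Mirror image, POINT participants whose overdose return falls on a control shift, at the plan's 6% rate with all returns to participating EDs: 356 × 0.06 × 0.5 = 10.7.

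Returns for withdrawal, abscess, endocarditis or intoxication would add to these figures. The documents give no rate for them.

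**4. What coach contact at an overdose return can change.**
- Binary overdose endpoint: nothing; the event has occurred.
- Time to relapse (first overdose ED visit or overdose death, section 9.4.3): nothing, for the same reason.
- ED admissions, scaled as binary in 9.4.3: nothing; the return visit is itself an ED presentation.
- MOUD engagement and duration, inpatient admission, Medicaid enrollment, child welfare and incarceration: these can still change after the visit, so the contrast can be diluted.

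**5. Primary-endpoint dilution, as sensitivity only.** This needs POINT to reach a control at a non-overdose return before any overdose. Let c be the share of controls so reached, each taking the full effect. The control rate becomes 0.12 − 0.06c.

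| c (assumed) | control rate | power at 356 per arm | n per arm for 80% |
|---|---|---|---|
| 0 | 12.0% | 80.0% | 356 |
| 5% | 11.7% | 76.5% | 389 |
| 10% | 11.4% | 72.5% | 427 |
| 20% | 10.8% | 63.7% | 524 |

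**6. Repeat records, as sensitivity only.** If 5% of records were repeats, distinct persons per arm would be 356 × 0.95 ≈ 338 and power 77.9%. At 10% they would be 356 × 0.90 ≈ 320 and power 75.7%. This counts only the lost persons, not the correlation between a person's two records.

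**The case against.** Several parts of the protocol lean toward one record per person. Section 9.3 speaks of participants, which means persons, and 9.2 counts patients. Section 7.3 places data collection at a single time, and 1.1 and 4.1 describe one structured interview. Section 10.1.3 gives each participant one identification number linked to the name. Under 10.1.8 the project manager reviews every record and compares names of naloxone-treated patients with the enrollment list. A reader might infer from 9.3 that every consent must be analyzed as a separate record, or that double enrollment took place; the documents support neither. But none of this text is a rule. The name check looks for missed patients, different staff cover the two kinds of shift, and controls are not told the full purpose of the study (10.1.1.2), so they cannot be expected to raise the conflict.

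A reader might also infer that 6% of controls dilute the primary comparison, or that every returning control receives POINT. The first fails because those controls already have the event. The second goes beyond the text: coaches engage patients, section 6.1.2 starts POINT after enrollment and services depend on the patient's interest. Contact is possible, not automatic.

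Finally, in a pragmatic trial, later service use by controls is part of real-world care. Comparison by assigned arm remains legitimate, and crossover of this kind pulls toward no difference. That stands for crossover. It does not answer repeat records. Section 9.2 also reports that enrollment stopped short and analyses were conducted, so a new exclusion may no longer have effect; de-duplication and reporting still would.

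**Conclusion.** The gap is real and should be fixed; it is not shown to invalidate the trial. The stated rules permit one person to enter twice, possibly in both arms, with overlapping windows, in an analysis that assumes independence. They also permit controls to be offered POINT during follow-up.

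Through overdose returns, about 21 controls (6%) is the most that would meet a coach, given the plan's 12% rate, half of shifts being POINT and all returns being to participating EDs; about 11 (3%) if half go elsewhere. That contact cannot alter the binary primary endpoint or time to relapse. It can weaken the contrast on MOUD engagement and duration, inpatient admission, Medicaid enrollment and other later secondary outcomes. The primary endpoint is exposed only through repeat records, former POINT participants re-enrolled as controls, and earlier non-overdose returns. The documents give no frequency for any of these, so the power losses in the sensitivity calculations rest wholly on assumed shares.

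**What to change.** - **Section 5.2:** if enrollment is open, add previous enrollment in this trial as an exclusion.
- **Section 6.3:** state that a participant keeps the first assigned arm, and that later ED visits are outcomes and never new index visits. This governs enrollment and analysis; it need not restrict any service that a site offers.
- **Section 9.3:** analyze one record per person, the first enrollment. The honest broker removes duplicates through its identification key. Section 10.1.3 has that key destroyed when the study concludes, so the check must be done before then.
- **Reporting:** give the number of repeat enrollments found and, from the coaches' service records, the number of controls who later received POINT. Keep those controls in their first assigned arm.

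The cost is one criterion, a sentence or two in 6.3 and in 9.3, and one duplicate check. The downside is slightly fewer records counted toward the enrollment goal.

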### 5.3 LIFESTYLE CONSIDERATIONS

Not applicable.

### 5.4 SCREEN FAILURES

Screen failures are defined as participants who consent to participate in this study but are not entered into the study because they do not meet the inclusion or exclusion criteria (i.e., failure of screening). If research staff or recovery coaches learn that the clinical information provided for someone previously consented to the study was inaccurate (for example, if a research staff member learns from a participant during their baseline assessment that their admission to the ED was non-opioid related and that the participant does not use opioids), data collection will be discontinued, and the participant will be excluded from the study. The patient will still be provided with the related study compensation for their time.

### 5.5 STRATEGIES FOR RECRUITMENT AND RETENTION

Individuals who are admitted to the ED for either an opioid overdose OR an opioid-related health issue will be deemed initially eligible, and the research personnel will be alerted of their presence in the ED. Research staff will also verify that the patient is at least 18 years of age. Once the initial eligibility is determined per the medical staff (reason for admission and at least age 18), either the recovery coach or the research assistant will approach the patient to inform them of study. This interaction will occur in the room in which they are receiving care in the ED, which is confidential area of the ED. They will use this initial meeting to explain the study and to ask the patient the questions from the opioid use disorder screening tool. If the patient scores at least a "1" on the opioid use disorder screening tool, they will be initially eligible for the study. They will then provide a brief overview of who they are and what the POINT study involves.

Because this initial interaction will occur prior to their discharge clearance, the research staff or recovery coach will reiterate to the patient that the research study is not a part of the treatment plan, and the patient may decline the study without impacting their treatment. Further, this "pre-discharge clearance" interaction will not hinder the discharge process; rather, we will utilize the "down time" the patient experiences while waiting in the ED. Once this initial discussion is complete, and if the patient chooses to take part, the research staff will return to the patient once he or she has received medical clearance for discharge from the ED and will move forward with the consent process.

Participants receive a \$30 gift card for their participation in the study. Research staff or recovery coaches will inform patients of this while explaining the study to the patient. The incentive is received at the end of their study visit.

Retention strategies are not applicable to the study, as participant will only be followed longitudinally through secondary administrative data.

## 6 STUDY INTERVENTION(S) OR EXPERIMENTAL MANIPULATION(S)

[figure not shown]
### 6.1 STUDY INTERVENTION(S) OR EXPERIMENTAL MANIPULATION(S) ADMINISTRATION

#### 6.1.1 STUDY INTERVENTION OR EXPERIMENTAL MANIPULATION DESCRIPTION

This study includes both an intervention and control condition.

The POINT intervention utilizes the services of a recovery coach (i.e., someone certified by the Indiana Counselors' Association on Alcohol and Drug Abuse to deliver recovery supports who has lived experience with addiction). The recovery coach meets patients in the ED after they have been revived from an overdose or are admitted to the ED for an opioid-related health issue, including opioid withdrawal, abscess (from IV opioid use), endocarditis (from IV opioid use), or active opioid intoxication. The

#### Conceptual Model for Project POINT

recovery coach offers the patient a range of evidence-based services including a brief assessment of high-risk behaviors, Hepatitis C and HIV testing, harm reduction counseling informed by motivational interviewing, and treatment referrals with follow-up to either a MOUD provider, detoxification services, or an inpatient treatment setting—with most patients choosing MOUD referral. Patients are also offered a take-home naloxone kit (i.e., the overdose reversing drug, which is offered as part care delivered by the recovery coach) and assistance with Medicaid enrollment, if applicable. Close collaboration with the local community mental health provider ensures POINT patients have their first assessment for MOUD within 1-2 business days of ED discharge.

Grounded in the concept of critical time intervention, recovery coaches provide over the phone or in person support to navigate barriers to care throughout the recovery process. Recovery coaches also offer to accompany patients to intake appointments or criminal justice and child welfare meetings as part of the standard care they deliver. Recovery coaches reach out to the client every 2-3 days, initially, until the patient is successfully engaged in recovery services. The entire care transition process takes between 2 weeks and several months, and POINT leaves the door open so patients can re-engage at any point they require help overcoming recovery barriers. Recovery coaches do not collect data for study purposes during this time; rather, any information they collect will be solely for the purposes of providing professional care as a recovery coach.

The control condition refers to standard care within the ED, in which patients receive a list of available local treatment options for opioid use disorder.

---

#### 6.1.2 ADMINISTRATION AND/OR DOSING

The POINT intervention begins immediately following enrollment, at which point the recovery coach begins speaking with the participant about recovery support services. Depending on the needs and desires of the client, the recovery coach customizes the delivery of his or her services to aid the participant in getting the resources they need to support recovery. Once the participant leaves the hospital, the recovery coaches attempt to remain in contact and reaches out to the participant every 2-3 days initially or until the patient is successfully engaged in recovery services. The process will depend on the client's interest and engagement, but the recovery coach often works with them for a period of weeks or months. POINT recovery coaches intentionally make room for open communication and re-engagement so patients can ask for help overcoming recovery barriers.

Following the patient's exit from the hospital, the recovery coach attempts to make additional contact. If recovery coaches are unable to immediately reach the patient, they complete the following steps.

- They continue to attempt follow-up calls, emails, texts for 2 weeks. The number provided could belong to another individual or be temporarily or permanently out-of-service or disconnected. The recovery coach will continue to follow-up, as the phone status might change, and make an attempt to call each person at least once a day during the 2-week time period.
- After two weeks, the recovery coach will stop trying to engage the patient. If the recovery coach has the opportunity to send an email or text or leave a voice mail, they will inform them the participant they are going to stop trying to call them but give them their contact information if they decide they need assistance with anything.
- If they reach an individual aside from the patient (e.g., mom, dad, spouse), the recovery coach will state that they are calling from IU Health and that they are attempting to reach the patient's name. No details of the study or the context of call will be provided to the individual.

If the recovery coach is able to reach the patient, and the patient indicates they want services, the recovery coach will provide individualized services while considering the following.

- The recovery coach will make sure all recovery avenues are open to the client such as medication for opioid use disorder (MOUD) (e.g., ensuring they are aware of methadone, Suboxone, and Vivitrol availability) and abstinence-based treatment.
- The recovery coach will discuss the evidence, benefits, and drawback of each type of treatment with the patient.
- The recovery coach will make sure the right resources are in place when connecting the patient to care, including payment source, insurance, and transportation.
- The recovery coach should continue to provide personalized support based on the needs of the patient.

POINT uses a warm handoff model, which means that recovery coaches:

- work to link patients to appropriate substance use disorder treatment and recovery supports,
- should obtain a health information release from the provider to which the patient is referred, and it should cover 12 months,
- continue to follow-up with the patient after they are connected to other supports for anywhere from 2 weeks to 3 months, depending on the patients' level of need and comfort with the services they were linked to, and
- allow patients to reengage with POINT services at any time for any reason if they need support in their recovery.

